3.7.2 Statistical Analyses of Secondary Endpoints

Except for the primary analyses there are no explicit or implied hypotheses in the protocol. Changes in the secondary outcomes are of interest as they will relate to efficacy as measured by the primary outcome variable. All analyses are descriptive and are intended to document the changes in these important variables. Secondary outcomes will be used to support the decision for efficacy of islet transplantation in this population but are not intended to be used explicitly for making a decision for the efficacy of islet transplantation in this population.

3.7.2.1 Subgroup analysis

CIT-07 is a multi-center single arm clinical trial to estimate the probability of achieving the endpoint at one year after enrollment (called “favorable outcome”). The primary analysis is described in SAP Section 3.7.1 and assumes no between-center variability: the response is a single binomial response of the total number of favorable outcomes among the total number of subjects enrolled. This assumption in the primary analysis of no between-center variability implies that the underlying success probability is the same at each center. Data from CIT centers are consistent with this assumption of no between center variability. In addition, the specification of a common protocol for manufacturing the islets and a common protocol for transplantation are also consistent with there being no between-center variability.

However, in order to examine the assumption of no between-center variability and to assess the rate of favorable outcome at each center, a Bayesian random effects model will be implemented. The rate of favorable outcome at each of the centers preparing islet cells for transplant will be estimated as a planned subgroup analysis using a Bayesian random-effect model under the assumption that the favorable outcome rates are *a priori* exchangeable. That is before any subjects are enrolled the centers are assumed to be similar (exchangeable) but, after data are analyzed, may be different. A one-sided 90% probability interval will be constructed to estimate a 90% posterior probability lower bound for efficacy at each center. The following section describes the methods to be used and provides supporting power calculations. A complete description, including the programs, is given in SAP Appendix 8.

This subgroup analysis will have no bearing upon the efficacy and safety analyses conducted for the study as a whole. Therefore, Bayesian analysis will not be considered in the adjustments for multiplicity that are described later for the “Key Secondary Endpoints”.

The hierarchical nature of the model introduces a correlation structure between centers which allows the estimates for each manufacturing center to incorporate data from other manufacturing centers. Smaller standard errors will therefore be provided than through using only data from each center in isolation from data from other centers. The estimates are adjusted towards the average success rate in all centers (also known as shrinkage estimators). The adjustment to the overall success rate depends on the variability observed in the actual data realized in the study and the sample sizes in each center.

If the data from the centers are similar to each other, then this is consistent with there not being very much between-center variability and there will be more shrinkage to the

overall analysis. If any of the centers are different from the others and have a different rate of favorable outcome the analysis will adapt, and there will be less shrinkage to the average rate of favorable outcome.

The trial data will be analyzed using the WinBUGS program [15]. Slightly different analyses result depending on exactly what prior assumptions are made. The distribution on the between-center variability is important to specify carefully, because default improper prior distributions are not appropriate and lead to unstable estimation. A prior distribution on the between center variability therefore is assumed. The particular prior distribution chosen, a gamma distribution on the inverse of the variance, is not very informative, but contains enough information to make the analysis robust and stable. The prospective data from CIT-07 will therefore stand alone in all but the assumptions on the variability between centers.

The hypothetical data sets in Appendix 8 were analyzed using WinBUGS. Unless stated otherwise, the simulations in this section and Appendix 8 were generated using the R program [16] and OpenBUGS [17], with the BRugs interface to call OpenBUGS from R. In a few cases (involving extreme cases where individual centers may have results of 100% or 0% favorable outcomes), R2WinBUGS was used to avoid some complications where the sampler failed to satisfy convergence diagnostics, in which case those cases were not included in the calculations (less than 2% of the simulations).

3.7.2.1.1 *The model and notation*

Suppose there are k centers and each center recruits n_i subjects, $i=1, \dots, k$: it is anticipated that $k=6$ and $(n_1, n_2, n_3, n_4, n_5, n_6) = (12, 12, 6, 6, 6, 6)$. Let y_i denote the observed number of favorable outcomes at center i out of n_i subjects, and let p_i denote the true underlying success probability at the i th center. The random-effects framework postulates that the observed number of successes for each center, y_i , conditional on p_i , is a draw from a binomial distribution, independently at each center:

$$y_i | p_i \text{ is Binomial}(n_i, p_i)$$

for $i=1, \dots, k$. Further denote the log odds of success at each center by θ_i

$$\theta_i = \log[p_i/(1-p_i)]$$

for $i=1, \dots, k$. Furthermore, assume that there may be between-center variability, but all centers are exchangeable: let θ_i given μ and σ^2 be like a sample from a normal population:

$$\theta_i | \mu, \sigma^2 \text{ is } N(\mu, \sigma^2).$$

The values μ and σ represent the population log odds and population between-center standard deviation of the log-odds respectively.

Let $\pi = e^\mu / (1 + e^\mu)$, the inverse log odds transformation, then π is the population probability of favorable outcome, the underlying predicted success probability for the population of centers.

A Bayesian approach, using Monte Carlo Markov Chain (MCMC) methods, will be implemented to estimate parameters and hyperparameters. The parameters of direct

interest are: the overall probability of favorable outcome π , and each of the probabilities of favorable outcome at individual centers p_i , $i=1, \dots, k$.

3.7.2.1.2 *The prior distribution*

The analysis of the CIT-07 data uses a very vague prior distribution with the distribution of μ assumed uniform and the distribution of σ^{-2} , denoted as τ , assumed to have an independent and proper gamma distribution with a large standard deviation. Specifically, τ has a density proportional to $\tau^{\alpha-1} e^{-\beta\tau}$ for $\tau > 0$ [18, p. 39]: values of $\alpha=2$ and $\beta=1.5$ are specified for analysis. These values lead to stable estimation and are consistent with having very little prior information on the between center variability [19]. The location of the prior mean of the precision is also approximately consistent with historical data and the variance has been inflated to represent uncertainty.

The gamma prior distribution for τ has a mean of α/β and variance of α/β^2 . The distribution of the θ_i 's given μ is a scaled t-distribution [18, p. 42]. If, for example μ corresponds to a mean for all centers of $\pi = 0.7$, then the conditional prior distribution of any of the p_i (that is the distribution of $p_i|\mu$ is such that it lies between 0.17 and 0.96 with probability 0.95, see SAP Appendix 8.1).

An additional setting of $\alpha=2$ and $\beta=0.75$ is examined in detail in Appendix 8.1. This gives a smaller prior mean value for the between center variability, which typically leads to more shrinkage towards the overall mean.

3.7.2.1.3 *Estimation of rate at individual centers*

Twelve subjects at one center is considered sufficient to demonstrate comparable efficacy at that center. This is based on the power calculations given in SAP Appendix 8.1.

Two methods for the estimation of the rate at individual centers are used: 1) estimation based on the complete set of endpoint data from CIT-07 centers using data from CIT protocols 02, 03, 04, 05, 06, and 07 and 2) estimation based on the endpoint data from CIT-07 centers using data from CIT-07 alone.

3.7.2.1.3.1 *Estimation of the rate at individual centers based on the complete set of endpoint data from CIT-07 centers using data from CIT protocols 02, 03, 04, 05, 06, and 07*

Those CIT-02, -03, -04, -05, -06, and -07 subjects enrolled at a CIT-07 participating center are assessed for meeting the CIT-07 primary endpoint definition. If a center enrolls at least 12 subjects from the combination of the CIT-02, -03, -04, -05, -06, and -07 protocols, the criteria for evaluations of that center require that the resulting analysis satisfy both (a) and (b) below:

- a) The overall primary result of the combined protocols is positive: that is, the primary analysis, which constructs a one-sided 95% confidence interval for the overall probability of favorable outcome assuming no between center variability, rules out a favorable outcome rate of 0.50 or less.
- b) The favorable outcome rate at that center, under the Bayesian model, is estimated to be at least 0.45 with posterior probability 0.90. That is, the lower 90% probability bound is at least 0.45.

3.7.2.1.3.2 Estimation of the rate at individual centers based on the endpoint data from CIT-07 centers using data from CIT-07 alone

The subgroup analysis described in SAP section 3.7.2.1.1 will also be fit to a dataset comprised of the CIT-07 subjects alone. If a center enrolls at least 12 subjects in CIT-07, the criteria for evaluations of that center require that the resulting analysis satisfy both (a) and (b) below:

- a) The overall primary result of CIT-07 is positive: that is, the primary analysis, which constructs a one-sided 95% confidence interval for the overall probability of favorable outcome assuming no between center variability, rules out a favorable outcome rate of 0.50 or less.
- b) The favorable outcome rate at that center, under the Bayesian model, is estimated to be at least 0.45 with posterior probability 0.90. That is, the lower 90% probability bound is at least 0.45.

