2.4 Sample Size and Power Calculations

The primary outcome (favorable outcome) is defined as the dichotomous event HbA1c $<7.0\%$ at Day 365 AND free of severe hypoglycemic events from Day 28 to Day 365, inclusive, following the first islet transplant, with Day 0 designated as the day of transplant. The sample size assessment and power calculations are based on the rate of this favorable outcome.

Historical data were available on a total 131 islet alone transplants performed at the University of Alberta, the University of Miami, the University of Minnesota, the University of Pennsylvania, Emory University and Northwestern University. A summary of the observed favorable outcome rates are presented in the following table.

Table 1 - Favorable outcomes in the six participating clinical centers

Center	Number of Subjects Transplanted	Number with favorable outcome	Percent with favorable outcome
University of Alberta	68	49	72
University of Miami	21	17	81
University of Minnesota	20	16	80
University of Pennsylvania	9	6	75
Emory University*	8	7	88
Northwestern University*	5	4	80
Total	131	99	76

*co-investigator institutions

The observed favorable outcome rate is higher than 70% for all centers. To determine sample size, we constructed exact one-sided 95% confidence intervals [8] for selected observed favorable outcome rates. These lower bounds are listed in Table 2. For a selected observed rate, we can be 95% confident that the true (but unobservable) favorable outcome rate is at least as large as the lower bound of the confidence interval. With 95% confidence, any rate less than the tabulated endpoint will be excluded as a potential value for the true favorable outcome rate.

Table 2 - The highest favorable outcome to be ruled out with 95% confidence

	Sample Size			
	24	36	48	60
Observed Favorable Outcome Rate	Lower Confidence Bounds for Exact One-sided Binomial Confidence Intervals For Favorable Outcome Rate (%)			
10%	1.5	3.9	4.2	4.4
20%	8.6	9.5	11.8	12.0
30%	14.6	18.2	18.6	20.4
40%	24.6	25.3	27.7	29.3
50%	31.9	35.3	37.4	38.7
60%	39.7	46.0	47.5	48.6
70%	52.1	54.5	58.2	58.8
80%	61.1	66.6	67.2	69.6
90%	76.0	76.3	79.3	81.2

The best clinical judgment of the investigators is that a 50% or larger favorable outcome rate would be clinically meaningful. Based on past experience we would expect to

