observe a rate larger than 70%. With a sample size of 48 transplanted subjects, 31 subjects (65%) would need to achieve a favorable outcome for the exact 95% lower confidence bound to rule out a 50% or lower true rate. (This result is not shown in the table; 65% favorable outcome rate of 48 subjects transplanted results in 31 successfully transplanted subjects). The proposed sample size is 48 subjects. Each participating center is expected to enroll at least 6 subjects.

Table 3 displays the probability that the study would conclude that the true favorable outcome rate is at least 50% for several selected values of the true favorable outcome rate. The tabulated probabilities are the power that a one-sided binomial test of the null hypothesis $H_0: p < 0.5$ versus the alternative hypothesis $H_a: p \geq 0.5$ would conclude that the true favorable outcome rate is at least 50% given that the selected value is the true underlying favorable outcome rate. These values are obtained by calculating the binomial probability that at least 31 out of 48 total enrolled subjects would achieve the favorable outcome given the true outcome rate.

Table 3- The power to rule out a favorable outcome rate that is less than or equal to 50% for the given true favorable outcome rate.

True Favorable Outcome Rate	Power to Rule Out Favorable Outcome Rate
10%	0.0000
20%	0.0000
30%	0.0000
40%	0.0005
50%	0.0297
60%	0.3111
70%	0.8359
80%	0.9962
90%	1.0000

This table shows that if the true favorable outcome rate is 70%, the power of concluding that the rate is over 50% is 0.8359 for a 5% level test.

3. General Analysis Definitions

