3.7.2.1.4 Power calculations ($\alpha=2$, $\beta=1.5$)

For any fixed value of the p_i s, binomial data can be simulated and the results analyzed and examined as to whether the criteria above are met. This will give an estimate of “power” where power is defined as the probability of meeting the criteria under various hypothesized parameter values.

For this section, we assume the sample sizes are two centers each with 12 subjects and 4 centers each with 6 subjects, for a total of $n=48$ subjects in CIT-07.

Preliminary data from CIT centers indicates a rate of favorable outcome between 70% and 90%.

For illustration therefore, suppose that $\pi = 0.70$ and there is no between center variability and so $p_1=p_2=p_3=p_4=p_5=p_6=0.70$. A total of 10,000 data sets were simulated and the proportion where criterion 1 was satisfied was calculated for an estimate of global power, as was the proportion where an individual center satisfied both criterion (a) and criterion (b) for an estimate of the individual center power. The individual power depends on the sample size in each group. The value for a centers with 12 subjects is 0.77 and is denoted as the individual power for a sample of size 12. A second simulation of 10,000 data sets was generated for $\pi = 0.70$ and gave the same result, and therefore 10,000 data sets were generated for other values of π . Results for the global power and the individual center power are given in Table 5.

Table 5 - Power and Size Estimation for $\alpha=2$ and $\beta=1.5$

Probability of Favorable Outcome at Each Center	Global Power	Individual Power (n=12)
0.5	0.03	0.025
0.7	0.84	0.77
0.8	1.00	0.98
0.9	1.00	1.00

The entries in this table can be interpreted as follows. If the true rate is 0.50 or less, there

is an appropriately low probability (0.025 or less) of a center meeting the criteria (corresponding to the concept of size or a type I error). If there is a high rate of favorable outcome, there is a high probability of meeting the criteria (corresponding to power): for a probability of 0.70, there is an individual center power of 77% and for 0.80, an individual center power of 0.98.

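### Twelve subjects are said to demonstrate comparable efficacy at a center, but the criteria and their power tables establish only a minimum rate

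*SAP*

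**What the plan says.** SAP section 3.7.2.1.3 says "Twelve subjects at one center is considered sufficient to demonstrate comparable efficacy at that center" and rests this on the power calculations of Appendix 8.1, which repeats the sentence. A center with at least 12 subjects is then evaluated on two conditions, once in the data pooled over CIT-02 to CIT-07 (3.7.2.1.3.1) and once in CIT-07 alone (3.7.2.1.3.2):

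- Criterion (a): the one-sided 95% interval for the overall rate, assuming no center effect, "rules out a favorable outcome rate of 0.50 or less".
- Criterion (b): "The favorable outcome rate at that center, under the Bayesian model, is estimated to be at least 0.45 with posterior probability 0.90". The SAP restates this as "That is, the lower 90% probability bound is at least 0.45".

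Power is defined in 3.7.2.1.4 as the probability of meeting these criteria. Section 2.4 records the investigators' judgment that "a 50% or larger favorable outcome rate would be clinically meaningful". Section 3.7.6.14 says that individual centers may use this subgroup analysis to support licensure of their islet preparation laboratories.

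**The concern.** Comparable is a relative word, but both criteria are absolute. Criterion (a) is about the pooled rate. Criterion (b) sets the center's rate against 0.45 whatever the study's rate turns out to be. The other centers affect a center's result only through the pooled gate and through shrinkage toward the common mean. A distance between the center and the rest is measured nowhere.

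So the sentence credits twelve subjects with a property that neither the rule nor its power tables address. A pass shows that the center's rate is probably at least 0.45. In a licensure file, comparable efficacy would be read as performance like that of the study.

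**Working it through.** **Inputs.** The layout is "two centers each with 12 subjects and 4 centers each with 6 subjects" (3.7.2.1.4). The prior has mu uniform and precision tau distributed Gamma(alpha=2, beta=1.5); these values "are specified for analysis" (3.7.2.1.2). For criterion (a), "31 subjects (65%) would need to achieve a favorable outcome" out of 48 (2.4). Criterion (b) is met when P(p1 < 0.45 | data) is at most 0.10. The true rate of the other five centers is an assumption: 0.90 is the top of the 70% to 90% range in 3.7.2.1.4, 0.80 is a middle value, and 0.76 is the historical pooled rate in Table 1 (99/131).

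**Formula.** y_i is Binomial(n_i, p_i) and logit p_i is N(mu, 1/tau). For every outcome vector y, P(p1 < 0.45 | y) was obtained by numerical integration instead of MCMC. Then

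Pass(p1, q) = sum over y of [product of binomial probabilities] × 1{total ≥ 31} × 1{P(p1 < 0.45 | y) ≤ 0.10}.

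**Reproducing the SAP (beta=1.5, 12-subject center).**

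| True rates | SAP | Recomputed |
|---|---|---|
| all 0.50 | 0.025 | 0.025 |
| all 0.70 | 0.77 | 0.769 |
| all 0.80 | 0.98 | 0.978 |
| center 0.5, others 0.7 | 0.31 | 0.308 |
| center 0.3, others 0.7 | 0.03 | 0.029 |
| center 0.5, others 0.9 | 0.40 | 0.387 |

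Agreement is within 2 points.

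**Probability that a 12-subject center below the others meets (a) and (b), beta=1.5.**

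| Others' true rate | 30 points below | 35 points below |
|---|---|---|
| 0.90 | 0.67 (center 0.60) | 0.53 (center 0.55) |
| 0.80 | 0.38 (center 0.50) | 0.26 (center 0.45) |
| 0.76 | 0.27 (center 0.46) | 0.17 (center 0.41) |

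The probability reaches 0.50 when the others are at about 0.84 (30 points) or 0.89 (35 points). Under the alternative prior, beta=0.75, those values are about 0.79 and 0.83.

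**Why the first row comes out as it does.** Let the others have 32/36 (11/12, 5/6, 5/6, 5/6, 6/6). The posterior P(p1 ≥ 0.45) is then 0.896 at 6/12 and 0.966 at 7/12. The rule is in effect 7 or more of 12:

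- P(Y ≥ 7 | 12, 0.60) = 0.665
- P(Y ≥ 7 | 12, 0.55) = 0.527

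Gate (a) is met about 99.9% of the time in these settings, so it adds nothing. A center at 7/12 (58%) against 32/36 (89%) passes: the total is 7 + 32 = 39, above 31, and 0.966 exceeds 0.90.

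**The SAP's own tables point the same way.** For a center truly at 0.50, Tables 5 and 6 give 0.025 when all centers are at 0.50, 0.31 when the others are at 0.70 and 0.40 when they are at 0.90. The pass probability rises as the gap widens. Most of that rise is gate (a), whose probability goes from 0.03 to 0.60 to 1.00. Stronger shrinkage alone moves the last figure from 0.40 to 0.58 (Table A3). Nothing in the rule counts against the gap.

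**Pooled data set.** The SAP gives no layout for CIT-02 to CIT-07 combined. Assuming six centers of 12 (gate (a) at 44 of 72), the 30- and 35-point figures are 0.72 and 0.60 with the others at 0.90, 0.41 and 0.28 at 0.80, and 0.29 and 0.18 at 0.76.

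**What a relative criterion would cost.** Suppose (b) were P(p1 > pi − d) ≥ 0.90, with gate (a) kept and beta=1.5. The margin d is an assumption.

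| d | Power, all centers 0.70 / 0.80 / 0.90 | Others 0.90, center 30 / 35 points below |
|---|---|---|
| 0.15 | 0.42 / 0.62 / 0.89 | 0.08 / 0.04 |
| 0.20 | 0.59 / 0.81 / 0.94 | 0.16 / 0.09 |
| 0.25 | 0.72 / 0.91 / 0.98 | 0.28 / 0.18 |

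Twelve subjects may or may not be enough for a comparative claim. It depends on a margin that the SAP does not set.

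**The case against.** The SAP is open about the behavior. Appendix 8.1 says that a center at 50% will meet the criteria if the others do well enough, Tables 6 and A3 print the 0.40 and 0.58, and 3.7.2.1 explains the shrinkage. An absolute floor is a legitimate design choice. The gap would also stay visible, because pi and every p_i are parameters of direct interest, and 3.7.1 and 3.7.6.14 call for center rates with exact intervals. Section 3.7.2.1 states that the subgroup analysis has no bearing on the study-level efficacy and safety analyses. All of this stands. It limits the consequence, but it does not make a minimum-rate rule a demonstration of comparability.

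Three stronger readings are tempting, and the document does not support them:

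- *A center 30 to 35 points below the others usually passes.* Under the specified prior this holds only when the others are at about 0.84 or more (30 points) or 0.89 or more (35 points). At 0.80 or 0.76 such a center fails more often than it passes.
- *The center is judged against 0.45 alone.* Gate (a) must also be met. It makes no comparison between centers, but it does bind when the others are at moderate rates.
- *The SAP declares a passing center comparable to the study as a whole.* That verdict appears only as superseded text in the summary of changes. The current sections call (a) and (b) criteria for evaluating a center and attach no such label. What remains is the comparable-efficacy sentence, with no comparator named.

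**Conclusion.** The point holds as a mismatch between claim and criterion. The current SAP says in two places that twelve subjects suffice to demonstrate comparable efficacy, while the rule and the power figures cited for it concern a pooled rate above 0.50 and a center rate of at least 0.45.

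How much this matters depends on how well the other centers do. With the others at 0.90, a center 30 or 35 points lower meets the criteria with probability 0.67 or 0.53. At 0.80 this is 0.38 or 0.26, and at 0.76 it is 0.27 or 0.17. These figures rest on the 12/12/6/6/6/6 layout, the beta=1.5 prior, and a common true rate at the other five centers.

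The primary analysis is unaffected. The correction is worth making because the analysis may support laboratory licensure, where the word comparable would carry weight that the criteria do not earn.

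**What to change.** In 3.7.2.1.3 and in Appendix 8.1 (Proposed Evaluation of Centers), replace the comparable-efficacy wording with a statement that twelve subjects are considered sufficient to demonstrate a favorable outcome rate of at least 0.45. Keep criteria (a) and (b) and the existing power tables, which already describe that claim.

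From the same MCMC run, report for each center the posterior median and lower 90% bound of p_i minus the mean rate of the other centers, as a descriptive result. This is one derived node in the BUGS code, for example (unweighted) p[i] − (sum(p[]) − p[i])/(N − 1). The text should say whether the mean is weighted by center size.

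Make no comparability claim unless a margin against the study's rate is prespecified and its power at n=12 is shown.

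The cost is two sentences, one line of code and one extra output per center. The downside is a narrower claim for each center.

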2.1 Study Design

This is a prospective, single-arm, multi-center study in islet transplantation. The centers participating in this phase 3 study will also undertake separate, phase 2 studies in islet transplantation, using innovative manufacturing and/or immunosuppressive regimens. In order to avoid bias in selection of subjects for these studies, eligible subjects will be randomized, prior to transplantation, to participate either in the phase 3 or a site-specific phase 2 study. The participating centers will treat a total of 48 study subjects accrued over 24 months in this phase 3 study.

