3.7.6.13 The proportion of subjects receiving a third islet transplant

For each subject, whether the third islet transplant is implemented will be observable at 365 ± 14 days following the initial and final infusion. The true rate of subjects who need a third islet transplant will be analyzed using the method for a binary outcome.

3.7.6.14 Proportion of subjects with HbA1c<7.0% and free of severe hypoglycemic events at each center preparing islets

Rates and 95% exact confidence intervals will be reported for each individual center. Rates will be reported at one year and two years after the final transplant. See subgroup analysis (SAP section 3.7.2.1) for the description of a more in depth analysis that may be

used by the individual centers to support licensure of individual islet preparation laboratories.

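### The combined-protocol center analysis pools other treatments under one rate per center and can pass when CIT-07 fails, so the stated size and power do not apply to it

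*SAP*

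**What the plan says.** SAP 3.7.2.1.3 plans two center analyses. In the combined one (3.7.2.1.3.1, repeated in Appendix 8.1), CIT-02 to CIT-07 "subjects enrolled at a CIT-07 participating center are assessed for meeting the CIT-07 primary endpoint definition". A center is evaluated once it has at least "12 subjects from the combination of the CIT-02, -03, -04, -05, -06, and -07 protocols", with no minimum number from CIT-07. It must then meet (a) "The overall primary result of the combined protocols is positive", meaning that the one-sided 95% bound on the pooled data excludes 0.50, and (b) a lower 90% posterior bound of at least 0.45 for that center. In the CIT-07-alone analysis (3.7.2.1.3.2), criterion (a) names CIT-07.

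Section 2.1 says that the centers will also "undertake separate, phase 2 studies in islet transplantation, using innovative manufacturing and/or immunosuppressive regimens". Section 3.7.2.1 supports equal center rates by "the specification of a common protocol for manufacturing the islets and a common protocol for transplantation". The model (3.7.2.1.1) and the WinBUGS code (Appendix 8.2) have one count and one rate per center. Section 3.7.2.1 also says that the CIT-07 data stand alone except for the prior on between-center variability. Section 3.7.6.14 says the subgroup analysis may be "used by the individual centers to support licensure of individual islet preparation laboratories".

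**The concern.** With no protocol term, a center's rate in the combined fit is a mixture of its CIT-07 rate and the rate under whatever its phase 2 study gave. The common manufacturing and transplant protocol that supports homogeneity does not describe the pooled set. Criterion (a) no longer guards against this, because strong phase 2 results can carry the pooled test while CIT-07 misses its own.

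The operating characteristics offered for the rule (size of 0.025 or less at a true rate of 0.50, center power in Tables 5 and 6, and the sufficiency of 12 subjects) were all computed for 48 CIT-07 subjects with criterion (a) applied to them. Section 3.7.2.1.5 covers mixed-protocol centers only by assuming the same true rate in both protocols, and says their power cannot exceed the global power. At stake is whether a center's result, which may be put toward laboratory licensure, reflects the CIT-07 treatment.

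**Working it through.** **Inputs from the SAP.** CIT-07 sizes (12,12,6,6,6,6), total 48 (3.7.2.1.1). Model: y_i ~ Binomial(n_i, p_i), logit p_i ~ N(μ, 1/τ), μ flat, τ ~ Gamma(2, 1.5). Criterion (a): exact one-sided 95% lower bound above 0.50. Criterion (b): P(p_i ≥ 0.45 | data) ≥ 0.90.

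**Assumptions, because the SAP gives none.** Six phase 2 subjects at each of the six centers, so 48 + 36 = 84 pooled; phase 2 rate p₂ the same at every center.

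**Plan's own figures first.** P(Bin(48, p) ≥ 31) = 0.0297, 0.8359 and 0.9962 at p = 0.5, 0.7 and 0.8, matching Tables 3 and 5. Simulating data sets and integrating the posterior on a grid gives center power (n=12) of 0.025-0.026, 0.77-0.78 and 0.98, against 0.025, 0.77 and 0.98 in Table 5. The Table 6 row with center 1 at 0.5 and the rest at 0.7 gives 0.31 and 0.57, as stated.

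**What the pooled rate is.** With CIT-07 at 0.50 and p₂ = 0.9, a center with 6+6 subjects has a pooled rate of (6×0.5 + 6×0.9)/12 = 0.70. One with 12+6 has (12×0.5 + 6×0.9)/18 = 0.63. Overall it is (48×0.5 + 36×0.9)/84 = 0.67.

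**Combined criterion (a).** The smallest r with P(Bin(84, 0.5) ≥ r) ≤ 0.05 is 51. The pass probability is P(X + Y ≥ 51), X ~ Bin(48, 0.5), Y ~ Bin(36, p₂).

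**Both criteria, CIT-07 rate 0.50 at every center** (ranges span centers and separate simulation runs of about 4,000 data sets):

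| p₂ | Combined (a) | Center passes, current rule | Center passes if CIT-07 must also meet (a) |
|---|---|---|---|
| 0.5 | 0.03 | about 0.02 | 0.01-0.02 |
| 0.7 | 0.39 | 0.27-0.30 | 0.02-0.04 |
| 0.8 | 0.71 | 0.54-0.62 | 0.02-0.04 |
| 0.9 | 0.93 | 0.78-0.87 | 0.02-0.04 |

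At p₂ = 0.5 the size stays near the stated value, so the inflation comes from the treatment difference and not from the added subjects. With CIT-07 at 0.40 and p₂ = 0.9, CIT-07 succeeds with probability 0.0005, yet a center passes 0.41-0.52 of the time.

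**Other direction.** With CIT-07 at 0.70 and p₂ = 0.5, combined (a) passes 0.60 of the time against 0.84 for CIT-07 alone. A center passes 0.40-0.51 of the time, against 0.65-0.76 on CIT-07 data alone.

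**Power cap.** With both rates at 0.70, a center passes the combined rule 0.85-0.92 of the time, above the CIT-07 global power of 0.84. If the cap means the global power of Table 5, it fails even with equal rates.

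**Is requiring CIT-07 success enough?** Take one 6-subject center at a CIT-07 rate of 0.3, the others at 0.8, and p₂ = 0.9 (1,500 data sets). The poor center passes 0.77 of the time under the current rule, 0.74 with the CIT-07 requirement, 0.32 with a shared protocol effect as well (assumed N(0, 2²) prior), and 0.14 on CIT-07 data alone. The requirement repairs criterion (a), but criterion (b) is still judged on a mixture.

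**The case against.** Pooling is a deliberate and disclosed choice. The justification of changes gives its reasons (more power, no subjective choice of subjects) and pairs it with a CIT-07-alone refit, to show what the extra subjects do. That refit keeps the CIT-07 criterion. Section 3.7.2.1 says the subgroup analysis has no bearing on the efficacy and safety conclusions, and 3.7.2 calls the secondary analyses descriptive. All of this stands, and it limits the severity. It does not close the gap: no rule says which analysis governs when the two disagree, and the refit has criteria only for centers with 12 or more CIT-07 subjects, two of the six anticipated.

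The large pass rates need a phase 2 rate well above CIT-07. The SAP shows no such difference and does not describe CIT-06 at all. That also stands, and the figures are conditional on it.

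A reader might infer that the pooled analysis decides by default. Appendices 6 and 7 list eight centers, "Each participating center is expected to enroll at least 6 subjects", and 8 × 6 = 48 would leave no center with 12. The text does not support this: 3.7.2.1.1 anticipates six centers, two of them with 12, and nowhere is either analysis named as deciding. A reader might also infer that licensure of the CIT-07 product is at stake. Section 3.7.6.14 speaks only of optional use by individual centers for their own laboratories.

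**Conclusion.** The combined analysis does not estimate a center's CIT-07 rate when phase 2 rates differ, and its criterion (a) can be met when CIT-07 fails its primary analysis. The Table 5 size, the power cap in 3.7.2.1.5 and the stand-alone statement in 3.7.2.1 therefore do not describe it. Under the assumed 6 phase 2 subjects per center and a CIT-07 rate of 0.50, the chance that a center passes rises from about 2% to about 30%, 60% and 79-87% as the phase 2 rate goes from 0.5 to 0.7, 0.8 and 0.9. Requiring CIT-07 to meet (a) brings it to about 1-4%.

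It would go too far to say that pooling always favors centers: a worse phase 2 rate wrongly denies them. Nor is the trial's primary conclusion affected. Should-fix.

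**What to change.** 1. In 3.7.2.1.3.1 and Appendix 8.1, make criterion (a) for both methods that the CIT-07 primary result (3.7.1) is positive.
2. Name the CIT-07-alone center estimate as the governing one. Report its lower bound for every center, including those with fewer than 12 CIT-07 subjects, and treat the pooled fit as supportive.
3. If pooled data are to inform criterion (b), add a protocol effect with a stated proper prior, or one shared effect of phase 2 versus CIT-07, and judge (b) on the center's CIT-07 rate. An unrestricted effect for a protocol run at a single center adds nothing: the fit reduces to CIT-07 alone. Do not rest the term on randomization between protocols for CIT-06, which the SAP does not describe.
4. State that the size and power in Tables 5 and 6 apply to the CIT-07-alone analysis only, and correct the stand-alone statement in 3.7.2.1 and the power statement in 3.7.2.1.5 (repeated in Appendix 8.1).

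Items 1, 2 and 4 are wording. Item 3 needs a prior, a code change and new simulations. The price is wider center intervals and lower center power than naive pooling gives.
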